APPENDIX 5: SHORT FORM 36V2 AUSTRALIAN VERSION

INSTRUCTIONS:

Please answer every question. Some questions may look like others, but each one is different. Please take the time to read and answer each question carefully by filling in the bubble that best represents your response.

Example:

This is for your review. Do not answer this question. The questionnaire begins with question 1 below.

For each question you will be asked to fill in a bubble in each line, like this:

How strongly do you agree or disagree with each of the following statements?

	Strongly agree	Agree	Uncertain	Disagree	Strongly disagree
a) I enjoy listening to music.					
b) I enjoy reading magazines.					

Please begin answering the questions now.

1. In general, would you say your health is:

Excellent	Very good	Good	Fair	Poor
				

2. Compared to one year ago, how would you rate your health in general now?

Much better now than one year ago	Somewhat better now than one year ago	About the same as one year ago	Somewhat worse now than one year ago	Much worse now than one year ago
				

Please turn the page and continue.

3. The following questions are about activities you might do during a typical day. Does your health now limit you in these activities? If so, how much?

	Yes, limited a lot	Yes, limited a little	No, not limited at all
a) Vigorous activities, such as running, lifting heavy objects, participating in strenuous sports			
b) Moderate activities, such as moving a table, pushing a vacuum cleaner, bowling, or playing golf			
c) Lifting or carrying groceries			
d) Climbing several flights of stairs			
e) Climbing one flight of stairs			
f) Bending, kneeling, or stooping			
g) Walking more than a kilometre			
h) Walking several hundred metres			
i) Walking one hundred metres			
j) Bathing or dressing yourself			

4. During the past 4 weeks, how much of the time have you had any of the following problems with your work or other regular daily activities as a result of your physical health?

	All of the time	Most of the time	Some of the time	A little of the time	None of the time
a) Cut down on the amount of time you spent on work or other activities					
b) Accomplished less than you would like					
c) Were limited in the kind of work or other activities					
d) Had difficulty performing the work or other activities (for example, it took extra effort)					

5. During the past 4 weeks, how much of the time have you had any of the following problems with your work or other regular daily activities as a result of any emotional problems (such as feeling depressed or anxious)?

	All of the time	Most of the time	Some of the time	A little of the time	None of the time
a) Cut down on the amount of time you spent on work or other activities					
b) Accomplished less than you would like					
c) Did work or other activities less carefully than usual					

6. During the past 4 weeks, to what extent has your physical health or emotional problems interfered with your normal social activities with family, friends, neighbors, or groups?

Not at all Slightly Moderately Quite a bit Extremely

7. How much bodily pain have you had during the past 4 weeks?

None Very mild Mild Moderate Severe Very severe

8. During the past 4 weeks, how much did pain interfere with your normal work (including both work outside the home and housework)?

Not at all A little bit Moderately Quite a bit Extremely

9. These questions are about how you feel and how things have been with you during the past 4 weeks. For each question, please give the one answer that comes closest to the way you have been feeling. How much of the time during the past 4 weeks...

	All of the time	Most of the time	Some of the time	A little of the time	None of the time
a) did you feel full of life?					
b) have you been very nervous?					
c) have you felt so down in the dumps that nothing could cheer you up?					
d) have you felt calm and peaceful?					
e) did you have a lot of energy?					
f) have you felt downhearted and depressed?					
g) did you feel worn out?					
h) have you been happy?					
i) did you feel tired?					

10. During the past 4 weeks, how much of the time has your physical health or emotional problems interfered with your social activities (like visiting friends, relatives, etc.)?

All of the time Most of the time Some of the time A little of the time None of the time

11. How TRUE or FALSE is each of the following statements for you?

	Definitely true	Mostly true	Don't know	Mostly false	Definitely false
a) I seem to get sick a little easier than other people					
b) I am as healthy as anybody I know					
c) I expect my health to get worse					
d) My health is excellent					

THANK YOU FOR COMPLETING THIS QUESTIONNAIRE!

OFFICE USE ONLY

Reason for questionnaire non-completion:

APPENDIX 6: EQ5D (ENGLISH VERSION FOR AUSTRALIA)

By placing a tick in one box in each group below, please indicate which statements best describe your own health state today.

Mobility

I have no problems in walking around PLEASE TICK

I have some problems in walking around ONE BOX

I am confined to bed

Personal Care

I have no problems with personal care PLEASE TICK

I have some problems washing or dressing myself ONE BOX

I am unable to wash or dress myself

Usual Activities *(e.g. work, study, housework, family or leisure activities)*

I have no problems with performing my usual activities PLEASE TICK

I have some problems with performing my usual activities ONE BOX

I am unable to perform my usual activities

Pain/Discomfort

I have no pain or discomfort PLEASE TICK

I have moderate pain or discomfort ONE BOX

I have extreme pain or discomfort

Anxiety/Depression

I am not anxious or depressed PLEASE TICK

[figure not shown]
I am moderately anxious or depressed ONE BOX

I am extremely anxious or depressed

To help people say how good or bad a health state is, we have drawn a scale (rather like a thermometer) on which the best state you can imagine is marked 100 and the worst state you can imagine is marked 0.

We would like you to indicate on this scale how good or bad your own health is today, in your opinion. Please do this by drawing a line from the box below to whichever point on the scale indicates how good or bad your health state is today.

**Your own
health state
today**

APPENDIX 7: DIFFUSE VERSUS FOCAL ARDS SUBSTUDY

This is a study to determine if acute respiratory distress patients with different subtypes behave differently.

Background & rationale

Patients with different subtypes of ARDS (focal, diffuse and patchy (on Chest X Ray)) may behave differently with application of high vs low PEEP depending on the percent of recruitable lung and the amount of stress and strain during PEEP titration/recruitment.

Patients with diffuse ARDS appear to have more recruitable lungs (1), have a higher inflection point and require higher PEEP levels for adequate recruitment without causing over-distension whereas patients with focal ARDS develop over-distension with higher levels of PEEP and have less recruitable lungs (2,3). Accordingly, in patients with a focal distribution of loss of aeration (i.e., with atelectatic dependent lobes coexisting with aerated nondependent lobes), the use of high PEEP levels (15–20 cm H₂O) results in minimal alveolar recruitment in the dependent lobes but significant hyperinflation in the nondependent lung lobes. Patients with patchy ARDS lie in between the two above mentioned subgroups (Table 1).

	Incidence (n=71)	Mortality rate	Primary ARDS	Compliance (ml cm H ₂ O ⁻¹)	Lower Inflection Point (cm H ₂ O)
Diffuse	23% (16)	75%	82%	19±9	8.4±2
Focal	36% (26)	42%	50%	41± 21	4.6±2
Patchy	41% (29)	41%	79%	30±15	6.3±2.7

Table 1. Differences between the 3 subgroups of patients with ARDS (Puybasset et al) (2,4,5)

Patients can be identified *a priori* as either having focal, patchy or diffuse disease based on their chest radiograph at the time of ARDS diagnosis/ study inclusion. The PHARLAP study provides an excellent opportunity to prospectively examine the effect of PEEP and recruitment on lung injury in the different subgroups as there will measurement of blood and bronchoalveolar lavage cytokines levels as a part of the study.

Objectives

Aim

To investigate the effect of recruitment and high (PHARLAP) v low (conventional) PEEP levels on inflammatory markers in different subtypes of ARDS (based on CXR).

Hypothesis

Patients with diffuse ARDS, when randomized to the recruitment and high PEEP arm, will have lower inflammatory markers when compared to patients ventilated with conventional ARDSnet protocol (6) as used in the LOVS study (7).

Study outcome measures

Analyse the inflammatory outcomes based on the radiological type of ARDS.

Inflammatory markers will be measured by

- Baseline to day 3 change in IL-8 and IL-6 concentrations in non-bronchoscopic broncho-alveolar lavage
- Baseline to day 3 change in IL-8 and IL-6 concentrations in plasma

In addition we will also study the ARDS subgroups (based on CXR) on basis of response to recruitment (in the PHARLAP study group): i.e. recruitment manoeuvre responders - defined as patients who improve static lung compliance with recruitment manoeuvre (i.e. > 0 ml/cmH₂O) from baseline to day 2 and non-responders (Patients who do not improve static lung compliance) as patients with diffuse ARDS can be hypothesised to have more response with recruitment.

Study design

This will be a sub-study of all patients who are enrolled into the PHARLAP study. Informed consent is obtained for all patients enrolled in the PHARLAP study, the participant information and consent form includes details of the diffuse versus focal substudy.

[figure not shown]
Methods

A chest radiograph at the time of ARDS onset (as determined by the study coordinator at the study site) will be de-identified, given a unique study number and saved to the PHARLAP database available for qualitative analysis post-hoc. Each patient will also have blood and BAL sample collected at baseline and day 3.

At the completion of the study the patients will be divided into predefined subgroups – focal, patchy and diffuse ARDS by independent radiologists. Additional data required for this sub study is the ventilator settings at the time of each CXR (PEEP, tidal volume, peak airway pressure and plateau pressure and respiratory rate) and blood gases.

Once patient’s subgroups are identified (focal, patchy and diffuse) we will compare the subgroups of ARDS managed by intervention or control strategy with markers of lung injury (plasma and BAL IL8 and IL6 levels) and patient related outcomes such as ventilator free days and other clinical/patient centred efficacy outcomes (Primary and secondary outcomes of PHARLAP) (see study flow chart below).

Study Flow chart

Statistical considerations

As PHARLAP proposes to include 340 patients, based on previous studies (2,4,5,8) about one third of patients will fall into each group and this should still leave adequately sized groups of patients with focal, patchy and diffuse to study their influence on the PHARLAP primary outcome of number of ventilator free days at day 28 post randomisation, markers of inflammatory mediators, and several other secondary outcomes. With a total of 300 patients in the study based on data from [name] et al (8) –personal communication we will likely get 80-100 patients per subtype, which would mean approximately 40 to 50 patient in each arm per subgroup. This should give us a reasonable sample size for each subgroup, and whilst mortality differences or VFDs may be unlikely, the potential for differences in other outcomes is reasonable, beside it will generate hypothesis for future studies.

We plan to analyse the outcomes of the study by utilising the general linear model with each outcome primary and secondary outcomes (PHARLAP - primary and secondary outcomes analysed separately as the dependent variable while ventilation strategy (PHARLAP / control), CXR coding (diffuse, focal, patchy) will be entered as independent factors. Interaction between ventilation strategy and the CXR coding will also be studied in the model. Post Hoc analysis will be done between the various CXR and ventilation subgroups (it will compare the outcomes of the CXR subgroups (diffuse, patchy and focal) within and among the PHARLAP and control group).

Funding

Diffuse versus focal substudy is supported by a \$34 950 grant (ANZCA) for procurement of the Chest X rays, cost of independent radiological scoring, statistical advice and salary support for a research assistant based at the ANZIC-RC.

Publications

A separate publication following the main publication will be completed in the name of the PHARLAP investigators led by [name] and the PHARLAP writing committee.

References

1. Nieszkowska A, et al. Incidence and regional distribution of lung over inflation during mechanical ventilation with positive end-expiratory pressure. *Crit Care Med* 2004; 32:1496–1503
2. Puybasset L, et al. Regional distribution of gas and tissue in acute respiratory distress syndrome. III. Consequences for the effects of positive end-expiratory pressure. *Int Car Med* 2000;26:1215-1227

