Site personnel will enrol patients using an internet-based system hosted by the ANZIC Research Centre. Randomisation to either the PHARLAP group or the control group will be by permuted blocks and stratified for centre and for the cause of ARDS (direct or indirect)⁴⁸.

Co-enrolment

Co-enrolment of patients into other interventional studies will be decided by the PHARLAP and the co-enrolling study management committees on a case-by-case basis. Participants can be co-enrolled in observational studies.

PARTICIPATING STUDY SITES

To be confirmed

- Albury Wodonga Health
- CVICU, Auckland City Hospital
- DCCM, Auckland City Hospital
- Austin Hospital
- Barwon Health (Geelong Hospital)
- Flinders Medical Centre
- John Hunter Hospital
- King Abdulaziz Medical City for National Guard (Riyadh)
- Lyell McEwin Hospital
- Middlemore Hospital
- Nepean Hospital
- Northern Hospital
- Launceston
- Prince Charles Hospital
- Royal North Shore
- Royal Prince Alfred
- St Vincents Hospital (Dublin)
- The Alfred Hospital
- Wellington Hospital
- Wollongong Hospital

STUDY PROCEDURES

Commencement of mechanical ventilation strategy

Patients in both groups should be commenced on the assigned mechanical ventilation strategy as soon as possible (but no later than 4 hours) after randomisation.

Prior to changing the pre-randomisation mechanical ventilation settings to the assigned strategy, 3 tasks need to occur in the following order in both groups of patients:

1. Predicted body weight should be estimated.
2. Static respiratory compliance should be measured (see below).
3. Specimens of blood and BAL should be collected (see below) – after static respiratory compliance has been measured.

Estimation of predicted body weight:

Before setting up the ventilator strategy, the patient's predicted body weight must be determined. This should be estimated using a formula which requires height⁴⁹ (Appendix 1). If there has been no recent (last few days) measurement of height, the height should be estimated using a formula which requires measurement of the demi-arm span (Appendix 1).

Measurement of static respiratory compliance:

- The patient should be adequately sedated (no spontaneous breaths).
- An expiratory pause of 5 seconds should be set to measure intrinsic PEEP (PEEPi). If the 5 second pause can not be achieved (because the next breath occurs before the end of the pause), a shorter pause should be set.
- Total PEEP is calculated as PEEPi + set PEEP.

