Neither the combined open lung procedure nor independently performed SRMs should be performed at times other than this daily morning intervention.

The **lack of improvement in static lung compliance** definition will be met if the static lung compliance after the staircase recruitment manoeuvre on day 3 is lower than the static lung compliance assessed prior to the performance of the initial (day 1) combined open lung procedure. Any patient who meets this criterion will have no further combined open lung procedures or brief recruitment manoeuvres and should have the PEEP set on 15 cmH₂O (or higher if clinically appropriate) unless the patient meets the readiness for weaning criteria.

No combined open lung procedures or brief recruitment manoeuvres should be performed after day 5. If the patient has not met readiness for weaning criteria, the optimal PEEP should be set at 15 cmH₂O (or higher if clinically appropriate) unless the patient meets the readiness for weaning criteria.

Desaturation: We recommend patients receive a chest x-ray for significant persistent desaturation to rule out barotrauma before a brief recruitment manoeuvre or further combined open lung procedures are performed.

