- The PEEP should be increased to the maximum tolerated PEEP determined during the most recently performed SRM, left at that level for 2 minutes, and then immediately returned to the daily optimal PEEP determined by that same SRM.

If an oxygen desaturation ($\geq 2\%$ below the daily precise SaO₂ target) occurs with no clear precipitating event (ie. potentially a deterioration in lung function), the brief recruitment manoeuvre should be performed as follows:

- The PEEP should be increased to the maximum tolerated PEEP determined during the most recently performed SRM, left at that level for 2 minutes, and then immediately returned to 2.5 cmH₂O (rounded up by 0.5 if the ventilator does not use 0.5 cmH₂O settings) higher than the previous daily optimal PEEP set during that SRM.
- This new PEEP level should be considered the new daily optimal PEEP level for the subsequent part of that day until the next SRM is performed. The FiO₂ should then be decreased as required to maintain the SaO₂ aim.
- The PEEP should not be set higher than 25 cmH₂O at any time during the study (with the exception of the staircase recruitment manoeuvre).

Brief recruitment manoeuvres should not be repeated more frequently than 2 hourly and not more than a maximum of 4 manoeuvres per 24 hours.

Ventilation during patient transfers: Mechanical ventilation should continue to adhere to this PHARLAP group strategy during patient transfers (to diagnostic or therapeutic procedures outside the ICU) where possible. However if the patient receives mechanical ventilation using either a manual (hand-bagging) circuit or a transport ventilator that is not practically able to deliver the PHARLAP group mechanical ventilation settings, patients may be ventilated using alternative means whilst away from the ICU. Resumption of PHARLAP group mechanical ventilation (including performance of a brief recruitment manoeuvre if indicated)

should occur as soon as possible after the transfer. A brief recruitment manoeuvre will usually be required (see above on this page).

Specific measurements on Day 3 in the PHARLAP group

Patients in both groups should have 2 things measured on day 3:

1. Static respiratory compliance should be measured (see page 22 for technique).
2. Specimens of blood and BAL should be collected (see below) – **after** static respiratory compliance has been measured. The BAL should be collected using the same technique as was used at baseline.

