APPENDIX 3: SCHEDULE OF EVENTS

Assessments/ Procedures	Pre Randomisation/ Baseline	Day 1	Day 2	Day 3	Day 4	Day 5	Day 6 till liberation of mechanical ventilation	ICU discharge	Hospital discharge	Follow-up 28 days	Follow-up 90 days	Follow-up 6 months
Inclusion & Exclusion criteria	X											
Consent	X											
Randomisation	X											
Demographic data	X											
Height & weight measurement	X											
CXR	X											
Download CXR image	X											
Apache II score	X											
Apache III diagnosis	X											
SOFA score	X	X	X	X	X	X	X					
Ventilation observations	X	X	X	X	X	X	X					
Static respiratory compliance		X		X								
Combined open lung procedure		X*	X*	X*	X*	X*						

* Only for patients randomised to PHARLAP treatment group (combined open lung procedure)

Assessments/ Procedures	Pre Randomisation/ Baseline	Day 1	Day 2	Day 3	Day 4	Day 5	Day 6 till liberation of mechanical ventilation	ICU discharge	Hospital discharge	Follow-up 28 days	Follow-up 90 days	Follow-up 6 months
Sputum sample (BAL)		X		X								
Blood sample		X		X								
Adverse events		X	X	X	X	X	X	X				
Serious adverse events		X	X	X	X	X	X	X	X			
Survival status								X	X	X	X	
SF36V ₂												X
EQ5D												X

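### Appendix 7 defines recruitment responders by a day-2 static compliance value that the trial does not schedule, and its rule differs from the main trial's responder subgroup

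*Combined protocol and SAP*

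**What the plan says.** **Substudy definition.** Appendix 7, under Study outcome measures, adds an analysis of PHARLAP patients by response to recruitment. A responder is someone whose static compliance rises by more than 0 ml/cmH₂O with the manoeuvre, and the comparison runs "from baseline to day 2 and non-responders (Patients who do not improve static lung compliance) as patients with diffuse ARDS". Patients without an improvement are non-responders. The appendix expects more response in diffuse ARDS.

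**Main-trial definition.** The section on ongoing recruitment manoeuvres in the PHARLAP group judges lack of improvement by whether "static lung compliance after the staircase recruitment manoeuvre on day 3 is lower than the static lung compliance assessed prior to the performance"; the reference reading is the one taken ahead of the day-1 combined open lung procedure. Subgroup (c) under Subgroup analyses uses this definition to separate responders from non-responders. The same definition also decides whether recruitment manoeuvres continue.

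**When compliance is measured.** The section on commencing the ventilation strategy requires one measurement before the pre-randomisation settings are changed. The next is on day 3: "Patients in both groups should have 2 things measured on day 3", the first being static compliance. The row "Static respiratory compliance" in Appendix 3 is marked under Day 1 and Day 3 only.

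**How it is measured.** The patient must have no spontaneous breaths. An expiratory pause gives intrinsic PEEP, and after a wait an inspiratory pause gives plateau pressure. Compliance is tidal volume divided by plateau pressure minus total PEEP.

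**The concern.** A responder rule needs two readings. Appendix 7 names baseline and day 2, and only the first is planned. Whoever runs the analysis will have to choose a substitute: another day, an approximate compliance from routine readings, or the main trial's rule. Appendix 7 assigns the radiological subtypes at the completion of the study, so that choice could be made with outcome data in hand. Pre-specification is meant to remove this discretion.

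The two definitions also share the label of responder while meaning different things. A separate substudy paper is planned to follow the main publication, so the same patient could be counted as a responder in one and a non-responder in the other, with nothing to alert the reader.

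**Working it through.** No arithmetic bears on the main point, so the check sets the passages side by side.

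**Step 1. Is the second reading planned?**

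| Source | Static compliance readings |
|---|---|
| Commencement of mechanical ventilation strategy | Before the assigned strategy starts, both groups |
| Day 3 measurements, control and PHARLAP sections | Day 3 |
| Appendix 3 | Day 1 and Day 3 |
| Appendix 7, additional data | Ventilator settings at each chest film and blood gases; no static compliance |
| Appendix 7, responder definition | Needs baseline and day 2 |

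The planned set is {day 1 before strategy, day 3} and the required set is {baseline, day 2}. The baseline value is the day-1 reading; the day-2 value is not planned.

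**Step 2. Could the schedule table be misread?** The combined open lung procedure row fills Days 1 to 5, and the BAL and blood rows fall on Days 1 and 3, as the text requires. The compliance row has the same pattern as the BAL and blood rows and agrees with the procedures text. The gap on day 2 is therefore not a broken table.

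**Step 3. Compare the two rules.** Write C0 for the baseline reading, C2 for a day-2 reading and C3 for the day-3 reading after the staircase manoeuvre.

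| | Appendix 7 | Main trial, subgroup (c) |
|---|---|---|
| Responder | C2 − C0 > 0 | C3 − C0 ≥ 0 |
| Non-responder | C2 − C0 ≤ 0 | C3 − C0 < 0 |
| Unchanged compliance | Non-responder | Not a non-responder |
| Place in the day | Linked to the manoeuvre, but not placed before or after it | After the staircase manoeuvre |

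The labels conflict when C2 > C0 and C3 < C0, or when C2 ≤ C0 and C3 ≥ C0.

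**Step 4. Does replacing day 2 with day 3 settle it?** Not alone. If both rules then used the same reading, they would still disagree when C3 = C0. If they used different day-3 readings, they would also disagree whenever one reading lay above C0 and the other below. This is possible because the day-3 measurement section puts the reading before the BAL and a brief recruitment manoeuvre, but does not place it relative to that day's staircase manoeuvre. The main definition requires a value after the staircase manoeuvre.

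**Step 5. Number of patients.** The arm size assumes equal allocation: 340 / 2 = 170 PHARLAP patients. None has a scheduled day-2 value. For scale, Appendix 7 expects about 40 to 50 patients per arm in each radiological subtype if 300 are studied.

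**The case against.** Three counter-arguments have force.

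**The responder analysis is peripheral.** A reader might infer that the substudy's central question collapses. The documents do not support that. The aim and hypothesis in Appendix 7 concern inflammatory markers by radiological subtype. Those are measured from baseline to day 3, and the samples are scheduled. The responder comparison is introduced as an addition, is not a factor in the substudy's general linear model, and belongs to work described as generating hypotheses. This objection stands and limits the point.

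**Some day-2 information may exist.** A reader might also infer that no day-2 compliance could be obtained at all. That goes too far. Ventilation observations and a combined open lung procedure are scheduled on day 2, and ventilation parameters and open lung procedure details are among the variables collected. The case report form is not part of the documents, so its content is unknown. An approximate compliance might be derived. Still, no section plans this, and without the pauses and intrinsic PEEP it would not be the defined quantity. The extra ventilator settings in Appendix 7 are tied to chest films, and Appendix 3 marks a film only at baseline. The weaning section refers to whether compliance improved when acting on days 2 to 5, but it orders no measurement. What stands is that the value is unscheduled, not that it is unobtainable.

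**The tie difference is small.** It matters only when compliance is exactly unchanged, and the documents give no basis for saying how often that happens. The differences in day and in reading carry more weight.

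**Conclusion.** The point holds as an internal inconsistency in one additional, exploratory, single-arm analysis. As defined, that analysis cannot be run from scheduled data for any PHARLAP patient (about 170 under equal allocation). Its rule differs from subgroup (c) in time point, in handling of unchanged compliance and in stated timing relative to the staircase manoeuvre. How many patients would be labelled differently cannot be estimated from the documents, and no bias is quantified here.

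The conclusion assumes that the case report form adds no day-2 pause measurement beyond the schedule. The primary ventilator-free-day analysis and the substudy's inflammatory-marker comparisons are not affected. The correction should be made because it is cheap and removes an analyst's choice, not because the trial's main conclusions depend on it.

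**What to change.** In Appendix 7, Study outcome measures:

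1. Change the responder analysis from baseline to day 2 to baseline to day 3.
2. Use the same analysis definition as subgroup (c), including its handling of unchanged compliance.
3. State which day-3 reading is used relative to the staircase manoeuvre. This requires reconciling the lack-of-improvement definition with the day-3 measurement section, which does not say whether its reading comes before or after that manoeuvre.

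These changes concern analysis definitions only. The lack-of-improvement rule also governs whether recruitment continues, and nothing here calls for altering it as a treatment rule.

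The cost is a short edit to Appendix 7 plus a clarifying line on the day-3 reading, with no new measurement. The drawback is that response is judged a day later. Patients without a day-3 value, because they have died, been liberated from the ventilator or had the procedure omitted, cannot be classified. They should be reported as a separate category rather than assigned to either group.
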